### Practice using your breath to help your body deal with stress.

We can't always control what society or others say or do, or our immediate response, but we can control being able to recognize our emotions and helping ourselves transition to a calmer emotional state if we feel overwhelmed.

This exercise is about slowing down the breath. Slowing down the breath brings our heart rate down which can help our body feel less stressed. You can use this breathing exercise to help you calm down if you start to feel overwhelmed.

#### App navigation

At the top of the screen, users will see a navigation bar with the names of the different guides. The guides also appear as "cards" on the home screen that users can click on. The cards and navigation bar items are labeled with the names of the guides: "Gender," "Queerness," "Stress," "Internalized Stigma." Additional features of the website include a crisis disclaimer and a link to the footer where crisis resources are listed and a quick exit button on the top right that is accessible in one click.

**Strategies to Ensure Sample Diversity:** We will reach the population using social media ads on sites including Facebook, Tumblr, Instagram, Reddit, Jack'd, Grindr, and Twitter. Ad targeting within social media sites allows us to specify the age range and other socio-demographic characteristics of individuals who will see the ads based on the information they provide in their online profiles. We will develop ads that promote our target population's interest by including diverse images of youth (i.e., images of different ages, portraying diverse race/ethnicity), as well as using ad-targeting specific to socio-demographic characteristics (e.g., delivering Facebook/Instagram ads only to youth based on their age, race/ethnicity and sex) and interests (e.g., TV shows with LGBT themes). Ads will link interested individuals to the study screener where they may verify their eligibility or email the team if they have additional questions about the study.

**Data Collection & Retention:** SGMY will click on social media advertisements and be taken to a Qualtrics page containing basic study information and a short description of study activities. **Screening:** Interested individuals will be asked to consent to and complete an online screener. We will use this approach as one of our strategies for filtering fraudulent or duplicate entries. Individuals who do not meet the eligibility criteria will be thanked for their interest and automatically routed to the Google page. We will not indicate why they were ineligible to avoid unintentional disclosure and to protect against fraud.

**Consent:** Individuals who screened eligible and passed initial verification (see SOP-Applicant Verification.pdf) will be sent a link to the study consent form (a waiver of parental consent will be obtained for minor participants). SGMY who do not consent will be taken to a screen thanking them for their interest. **Baseline & Randomization:** Those who consent will complete the baseline survey. Study staff will perform a second round of verification once a baseline survey has been completed. Those who pass verification will be randomized 1:1 into the control or experimental condition. **Registration:** After randomization, participants will be sent a link to either the control condition website or the intervention web app. Once a participant registers for an account on the website or web app, they will receive their baseline incentive.

**Measures to protect against fraud and hacking:** We will use best practices to reduce the likelihood of online fraud: (1) Keep compensation sufficiently low (i.e., balance incentives with the effort required from respondents) to reduce the chances of respondents participating solely to gain incentive payments. (2) Cross-check information between the screener and baseline surveys (e.g., compare zip code entered on screener with City and State entered on baseline). This verification process is commonly used in online research and aims to prevent individuals from being enrolled in a study more than once, and to prevent bots from enrolling. (3) Verify IP address location is located in the United States. See "SOP-Applicant Verification.pdf" for detailed procedures.

## **2. Data Collection:**

Not applicable

## **3. Genetic Testing:**

Not applicable

## **4. Use of Deception:**

Not applicable

## **5. Statistical Analysis:**

Descriptive statistics of the psychosocial and demographic characteristics of the participants will be described for all and by intervention group. These will be compared between treatment groups using t-tests or Wilcoxon rank sum tests for continuous variables and chi-square tests for categorical variables.

Main intent-to-treat analyses will compare the experimental to the control group on self-assessed psychosocial outcomes immediately post-intervention, controlling for baseline values on those variables. For each construct (e.g. anxiety, depression, positive/negative emotions), a separate analysis will be used to evaluate the difference in magnitude of change from baseline to the week 4 follow-up assessment as a function of intervention condition (experimental vs control). We will also examine if there is a difference in change over time by examining the interaction of time by condition.

Descriptive statistics of the psychosocial and demographic characteristics of the participants will be described for all and by intervention group. We will also examine participants' web app usage, satisfaction with the web app, and how web app usage and satisfaction correlates with improvements in psychosocial wellbeing. We will report descriptive statistics for web app usage and satisfaction (e.g. means, medians, standard deviations, IQR), and will conduct pearson's or spearman's correlations to explore whether greater engagement with the web app (e.g. indexed by number of pages viewed, time spent in the web app) etc. is positively correlated with improvement in each outcome variable from week 0 to 4 within the experimental group.

In order to adequately power this trial to detect effects that are medium-in-size or larger (Cohen's  $d >= .50$ ), we plan to recruit 300 participants, and randomly assign them to conditions in a 1:1 fashion. Medium effect sizes are roughly in line with those observed in prior psychosocial interventions for SGM teens and young adults (Craig et al. 2012; Craig et al., 2021; Lucassen et al. 2015; Pachankis et al., 2015). A sample of 300 participants was selected to account for a non-compliance and/or attrition rate of up to 35% of the recruited sample, a rate which is in line with conservative estimates of participant attrition from the trials cited above. This sample size will serve as a buffer to ensure that any participant loss will not undermine the power of the statistical analyses. After accounting for the potential loss to follow-up, a sample size of ~97 participants per group is necessary in order to detect moderately small to medium effect sizes for a two-sample comparison of means.

For all analyses, data will be reported as aggregated groups, and no individual identifying information will be used.

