## **INTRODUCTION AND PURPOSE:**

The purpose of this study is to assess the psychosocial effects of a novel web application (web app) called “immi” (short for ‘i am me’), designed to provide sexual and gender minority youth (SGMY) with tools for affirming their identities and coping with minority stress. Prior research demonstrates that interventions that focus on providing SGMY with resources for adaptively coping with minority stress have the potential to improve their mental health and wellbeing. However, few digital resources exist to address this need. The goal of the proposed research is to test whether this novel and scalable web-based intervention has the potential to impact key psychosocial outcomes among SGMY ages 13-19, such as coping self-efficacy and symptoms of anxiety and depression. Please see the Background section of this application for more information.

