## **OBJECTIVES:**

Objective 1: To test whether SGMY randomly assigned to use the immi web app report significantly higher identity affirmation, subjective connectedness to the LGBTQ+ (Lesbian, Gay, Bisexual, Transgender, Queer/Questioning, and other sexual and gender minority identities) community, use of adaptive cognitive and behavioral coping skills, and psychosocial wellbeing (e.g. higher positive and negative affect, lower symptoms of depression and anxiety, and greater life satisfaction) than youth randomly assigned to a ‘resource list’ control group. The resource list control group will receive a list of technology-based psychosocial resources that are currently freely available to SGMY.

Objective 2: To assess how individual differences in usage and satisfaction with the immi web app relate to the outcomes listed in Objective 1, and to identify areas for further tool optimization. We will achieve this by linking web app usage data to outcome data, as well as through collecting quantitative and qualitative data measuring user satisfaction and suggestions for improvement.

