While prior research suggests that interventions that include these components may improve the mental health of SGMY, interventions have primarily been delivered within the context of time intensive, in-person sessions, limiting their reach. Many SGMY face significant barriers to accessing affirming in-person services, an issue that has been exacerbated by the COVID-19 pandemic. Digital technologies can be utilized to help bridge this gap by meeting a pressing need within a medium in which youth are already seeking support. Over half of SGMY report spending over five hours a day online, and SGMY are more likely than those who identify as heterosexual to report going online for health information, including for support with depression (76% vs. 32%) and anxiety (75% vs. 36%). However, to date, there is little research examining the efficacy of web-based platforms for helping SGMY cope with minority stress.

The proposed research seeks to fill this need by testing the efficacy of a web app for SGM ages 13-19. This web app is designed to facilitate SGM identity affirmation, promote a sense of connectedness to the LGBTQ+ community, and encourage cognitive and behavioral coping skill practice. This tool was built by Hopelab, a nonprofit social innovation lab, in collaboration with CenterLink, an international nonprofit organization and member-based association of LGBTQ (Lesbian, Gay, Bisexual, Transgender, and Queer) centers serving their local and regional communities. The goal of the proposed research is to assess the efficacy of this web app for improving key psychosocial outcomes among SGMY, such as coping self-efficacy and symptoms of anxiety and depression.

---

 Meyer, I. H. (2003). Prejudice, social stress, and mental health in lesbian, gay, and bisexual populations: conceptual issues and research evidence. *Psychological bulletin*, 129(5), 674.

 Craig, S. L., Austin, A., & McInroy, L. B. (2014). School-based groups to support multiethnic sexual minority youth resiliency: Preliminary effectiveness. *Child and adolescent social work journal*, 31(1), 87-106.

 Craig, S. L., & Austin, A. (2016). The AFFIRM open pilot feasibility study: A brief affirmative cognitive behavioral coping skills group intervention for sexual and gender minority youth. *Children and Youth Services Review*, 64, 136-144.

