## ***8. Investigator's Risk/Benefit Assessment:***

No more than minimal risk: The risks to research participants enumerated above are reasonable in relation to the anticipated increase in knowledge about LGBTQ+ identity and adaptive cognitive and behavioral coping skills. Our study is expected to result in a benefit to society since it will provide a basis of knowledge on the efficacy of a web app for improving key psychosocial outcomes among SGMY, such as coping self-efficacy and symptoms of anxiety and depression. Thus, the unlikely risks entailed by participation in this study are offset by its potential benefits.

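### Objective 1 is tested by a separate main analysis for each of about 8 to 11 outcomes or constructs, with no primary outcome, alpha, success rule or multiplicity control

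*Combined protocol and SAP*

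**What the plan says.** Objective 1 is worded as a hypothesis test: it asks whether youth "randomly assigned to use the immi web app report significantly higher identity affirmation", and continues with community connectedness, use of coping skills, and wellbeing. Wellbeing is illustrated by positive affect, negative affect, depression, anxiety and life satisfaction. That makes about 8 outcomes, because the wellbeing list is given only as examples.

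The Background section states the aim as efficacy: "The goal of the proposed research is to assess the efficacy of this web app for improving key psychosocial outcomes among SGMY". The Investigator's Risk/Benefit Assessment expects that the study "it will provide a basis of knowledge on the efficacy of a web app for improving key psychosocial outcomes among SGMY".

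Under Study Procedures, 5. Statistical Analysis, the confirmatory comparison is plural: "Main intent-to-treat analyses will compare the experimental to the control group on self-assessed psychosocial outcomes immediately post-intervention", adjusted for baseline. It is then divided: "For each construct (e.g. anxiety, depression, positive/negative emotions), a separate analysis will be used to evaluate the difference in magnitude of change" from baseline to week 4. A time-by-condition interaction is to be examined as well.

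The sample-size paragraph begins "In order to adequately power this trial to detect effects that are medium-in-size or larger" (d of at least 0.50) and ends by saying that "a sample size of ~97 participants per group is necessary in order to detect moderately small to medium effect sizes" in a comparison of two means. It ties neither figure to an outcome, an alpha or a power level.

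The nearest thing to a primary outcome is the recurring phrase "key psychosocial outcomes among SGMY ages 13-19, such as coping self-efficacy and symptoms of anxiety and depression". It is an open list of examples. Statistical Analysis does not call any of these outcomes primary, and its own examples leave out coping self-efficacy.

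**The concern.** Every construct's analysis has equal standing as a main analysis, and nothing says which result, or how many, decides whether Objective 1 is met. If one significant result among many were enough, the probability of declaring a benefit from an ineffective app would exceed the level used for each test, by an amount that the plan neither states nor limits. The documents also do not fix the headline outcome in advance, so it could be chosen after the results are known. Once outcome data have been seen, that choice can no longer be credibly prespecified.

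**Working it through.** **Number of analyses**
- Objective 1 names 8 outcomes: identity affirmation, connectedness, coping skills, positive affect, negative affect, depression, anxiety, life satisfaction.
- Study Instruments, counted by construct, gives 11: three psychological targets (identity, connectedness, coping), seven numbered wellbeing constructs, and substance use. 3 + 7 + 1 = 11.
- Study Instruments, counted by scale or subscale, gives 17: five identity measures, four community and coping measures, and eight wellbeing and substance-use measures. 5 + 4 + 8 = 17.

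Statistical Analysis works by construct, so 8 and 11 are the relevant counts and 17 is a sensitivity case.

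**The plan's own figure.** 300 × (1 − 0.35) / 2 = 97.5, which reproduces the stated figure of about 97 per group. No alpha or power accompanies it. Assuming two-sided 0.05, a two-sample t-test with 97 per group has 93% power at d = 0.50 and 79% at d = 0.40.

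**Chance of at least one false benefit.** Assumptions, none of them stated in the documents:
- two-sided 0.05 per test, so 0.025 in the beneficial direction;
- a beneficial direction defined for every outcome;
- no true effect on any outcome;
- normal test statistics with equal pairwise correlation r;
- any one significant result may be claimed.

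For k independent tests the chance is 1 − 0.975^k. With correlation r it is

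1 − ∫ Φ((1.96 − √r·u) / √(1 − r))^k φ(u) du,

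evaluated numerically.

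| Tests (k) | r = 0.3 | r = 0.5 | r = 0.7 | Independent |
|---|---|---|---|---|
| 1 | 2.5% | 2.5% | 2.5% | 2.5% |
| 8 (Objective 1) | 15% | 13% | 10% | 18% |
| 11 (constructs) | 19% | 15% | 11% | 24% |
| 17 (all scales; sensitivity) | 25% | 19% | 14% | 35% |

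The time-by-condition test and any separate analysis of coping subscales are left out of these counts.

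**Power cost of the remedy.** This is two-sample t-test power per outcome, before any gain from baseline adjustment. Holm over three outcomes starts at 0.05 / 3 = 0.0167. The value d = 0.40 is an assumed reading of the plan's smaller effect. The 120 per group is 150 × 0.80, from the plan's 80% retention target.

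| n per group | d | alpha 0.05 | alpha 0.0167 |
|---|---|---|---|
| 97 | 0.50 | 93% | 86% |
| 97 | 0.40 | 79% | 64% |
| 120 | 0.50 | 97% | 93% |
| 120 | 0.40 | 87% | 75% |

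**The case against.** The plan never says that one significant result is enough. Objective 1 joins its outcomes with a conjunction, and the analysis section commits to reporting every construct. If all outcomes had to be significant, there would be no inflation. This stands as far as it goes: the inflation is conditional. But the plan does not state an all-outcomes rule either, and the gap is the absence of any rule.

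The trial could also be called exploratory. It is a four-week, minimal-risk study, and some sections speak only of the app's potential to affect outcomes. Against that, the between-arm analyses are labelled main, Objective 1 asks for significance, and two sections state the aim as efficacy. The exploratory wording in Statistical Analysis is kept for the usage correlations. If exploration is intended, the plan should say so.

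A reader might infer a false-benefit chance of up to 25%. That requires all 17 scales to be separate main tests, including concealment motivation, outness and each coping instrument. No section says this; the planned unit is the construct.

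A reader might also infer that the sample size ignores multiplicity. The documents do not support so firm a statement, because the intended alpha and power are not given. At d = 0.50 there is some slack: under Bonferroni over 8 outcomes (alpha 0.05 / 8), 97 per group still has 76% power. At d = 0.40 it has 51%.

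**Conclusion.** The point holds for the 8 outcomes of Objective 1 and the roughly 11 constructs of the instrument section. Followed as written, the plan leaves the efficacy conclusion without a defined false-positive rate. That finding needs no assumption about alpha or correlation.

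Its size does. On the assumptions listed, the chance of at least one false benefit is about 10% to 19%, roughly four to eight times the 2.5% for one test. The 2.5% is itself an assumption and not a figure from the plan. The range of 14% to 25% for 17 scales is a sensitivity case only. Nothing here shows that the sponsor intends to select a favourable outcome; the documents simply do not prevent it. The matter should be settled before outcome data are seen.

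**What to change.** In Statistical Analysis, before outcome data are seen:

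1. State an overall two-sided alpha of 0.05.
2. Name one primary outcome, or a small primary family, chosen by the sponsor. One candidate family is the recurring set of key outcomes: coping self-efficacy (Stress Appraisals Measure for Adolescents), GAD-7 and PHQ-8.
3. Test a family with Holm or an equivalent family-wise procedure, and claim efficacy only for outcomes rejected in favour of immi.
4. Label all other scales secondary, reported as estimates with 95% confidence intervals or under false discovery rate control, with no efficacy claim.
5. Tie the power statement to the chosen outcome(s) and alpha.

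Amend Objective 1 to name the primary outcome(s) and the beneficial direction of each. It does not name coping self-efficacy at present, and as worded it counts an increase in negative affect as a gain.

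The cost is text only, with no extra participants or data. A single primary outcome loses no power. Holm over three loses the amounts tabulated above at its first step. The largest of these is the fall from 79% to 64% at d = 0.40 with 97 per group, which the sponsor should weigh when choosing between one outcome and a family.

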## **METHODS:**

### **1. Study Instruments:**

Participants will complete two online surveys during the trial (baseline and a follow-up survey on Day 28). Assessments will take 30-40 minutes to complete. Assessment measures fall into four categories: 1) psychological targets, 2) psychosocial wellbeing and mental health, 3) intervention acceptability and satisfaction, and 4) demographics and other baseline assessments.

Psychological Targets. The immi web app is designed to 1) affirm SGM identities, 2) promote a sense of connectedness to the SGM community, and 3) teach adaptive cognitive and behavioral coping skills. Aligned with our theory of change, we will measure psychological targets that map onto each of these three constructs at baseline and at follow-up.

Specifically, to measure change in SGM identity related constructs, we will administer the identity affirmation subscale from Lesbian Gay and Bisexual Positive Identity Measure. We will also administer the concealment motivation, internalized homonegativity, and acceptance concerns subscales of the Lesbian Gay and Bisexual Identity Scale. A single item measure of 'outness' to friends and family will be included to assess change in willingness to disclose one's SGM identity.

---

 Riggle, E. D., Mohr, J. J., Rostosky, S. S., Fingerhut, A. W., & Balsam, K. F. (2014). A multifactor lesbian, gay, and bisexual positive identity measure (LGB-PIM). *Psychology of Sexual Orientation and Gender Diversity*, 1(4), 398-411.

 Mohr, J. J., & Kendra, M. S. (2011). Revision and extension of a multidimensional measure of sexual minority identity: The Lesbian, Gay, and Bisexual Identity Scale. *Journal of counseling psychology*, 58(2), 234-245.

 Quinn, D. M., Williams, M. K., Quintana, F., Gaskins, J. L., Overstreet, N. M., Pishori, A., ... & Chaudoir, S. R. (2014). Examining effects of anticipated stigma, centrality, salience, internalization, and outness on psychological distress for people with concealable stigmatized identities. *PLoS one*, 9(5), e96977.

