#### **4. Administration of Surveys and/or Process:**

We will collect survey data via online self-completed Qualtrics surveys administered at baseline and 4 weeks. Participants will enter their own responses to questions directly into the survey on their personal computer, smartphone or tablet.

Individuals who complete the screener survey and are eligible will be sent a link to the informed consent form. Those who provide their consent will complete a baseline assessment which will take approximately 30-40 minutes. At the end of the 4-week active study period, participants will complete an online survey to assess key psychosocial outcomes. This follow-up survey will take participants approximately 30-40 minutes to complete.

The incentive for completing the baseline survey is \$30 and the follow-up survey incentive is \$40. These incentives are small enough to avoid coercion, yet sufficiently substantial to promote retention. In order for interventions to be evaluated as potential best evidence-based interventions through CDCs Prevention Synthesis Research activity, data must be available for at least a single follow-up time point for at least 70% of participants. As described below, a detailed retention plan for the study will draw on previously successful retention protocols to achieve at least an 80% retention rate for the follow-up survey.

If a participant does not complete their follow-up survey by Day 31, we will send a reminder message via email, SMS, or direct message via social media (depending on the participant's communication preferences). The participant will be recontacted using the same methods on Day 35, 39, and 42 if they still have not completed the survey. Each contact will be logged in a spreadsheet.

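### Does the added time-by-condition test undermine the baseline-adjusted Week 4 comparison that the plan calls main?

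*Combined protocol and SAP*

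**What the plan says.** Under Study Procedures, 5. Statistical Analysis, three sentences deal with the treatment comparison.

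- The first sets the main analysis: "Main intent-to-treat analyses will compare the experimental to the control group on self-assessed psychosocial outcomes" "immediately post-intervention, controlling for baseline values on those variables". This is an analysis of covariance (ANCOVA) of the Week 4 score on arm and baseline score.
- The second says that each construct has its own analysis, to "evaluate the difference in magnitude of change from baseline to the week 4 follow-up assessment as a function of intervention condition". It does not say whether the change is adjusted for baseline.
- The third adds the interaction: "We will also examine if there is a difference in change over time by examining the interaction of time by condition". No model, significance level or role is given.

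Methods, 1. Study Instruments, provides for two surveys only, at baseline and Day 28. The sample-size paragraph aims at effects of d = 0.50 or more ("In order to adequately power this trial to detect effects that are medium-in-size or larger"). It says that about 97 per group detects "moderately small to medium effect sizes for a two-sample comparison of means".

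**The concern.** With two time points there is no trajectory for an interaction to describe. In the usual model, with free baseline means and complete data, the time-by-condition term is exactly the between-arm difference in unadjusted change scores. Under randomization it estimates the same effect as ANCOVA, and its variance is never smaller. So the plan appears to put two p-values on one question for each outcome without stating which decides. The sentence on magnitude of change adds to the doubt, because it could mean ANCOVA or a raw change score.

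Two things would be at stake. If the interaction were taken as the deciding test, power would be lost, and at correlations below 0.5 it would be weaker than the plain two-sample comparison used to size the trial. If whichever test reached significance could be claimed, type I error per outcome would exceed 5%.

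**Working it through.** **Inputs.** From the documents: 300 randomized 1:1, so 150 per arm; loss of up to 35%; about 97 per group analysed; d = 0.50. Not in the documents, so assumed: two-sided 5% level; 80% power where needed; baseline to Week 4 correlation ρ from 0.4 to 0.8; equal SDs at both times; d = 0.40 as a reading of moderately small to medium.

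**The plan's own figure.** 300 × (1 − 0.35) / 2 = 97.5, which gives the stated 97. At 80% power the detectable effect is (1.960 + 0.842) × √(2/97) = 0.402, so d = 0.40 is a fair reading. An unadjusted comparison at 97 per group has 93.4% power at d = 0.50 and 79.2% at d = 0.40 (noncentral t).

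**Variance factors** (unit SD, 97 followed up per arm):

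- ANCOVA: 1 − ρ².
- Interaction, completers only: 2(1 − ρ). Ratio to ANCOVA: 2/(1 + ρ) = 1 + (1 − ρ)/(1 + ρ).
- Interaction in a likelihood-based mixed model with free baseline means, all 150 baselines per arm, follow-up missing completely at random: (1 − ρ²) + (97/150)(1 − ρ)². Ratio: 1 + (97/150)(1 − ρ)/(1 + ρ).
- Longitudinal model with baseline means constrained equal: about as precise as ANCOVA, ratio about 1.

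For example, at ρ = 0.4 the completers ratio is 2/1.4 = 1.43, and the mixed-model ratio is 1 + 0.647 × 0.6/1.4 = 1.28.

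| ρ | Ratio, completers | Ratio, mixed model | Power at d = 0.50: ANCOVA / completers / mixed | Power at d = 0.40: ANCOVA / completers / mixed |
|---|---|---|---|---|
| 0.4 | 1.43 | 1.28 | 96.6 / 88.5 / 91.7% | 85.6 / 71.6 / 76.3% |
| 0.5 | 1.33 | 1.22 | 97.9 / 93.4 / 95.2% | 89.3 / 79.2 / 82.7% |
| 0.6 | 1.25 | 1.16 | 99.1 / 97.2 / 98.0% | 93.4 / 87.3 / 89.5% |
| 0.7 | 1.18 | 1.11 | 99.8 / 99.4 / 99.6% | 97.3 / 94.7 / 95.7% |
| 0.8 | 1.11 | 1.07 | all about 100% | 99.6 / 99.2 / 99.4% |

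If retention meets the target ("to achieve at least an 80% retention rate for the follow-up survey"), 120 per arm remain. At ρ = 0.4, ANCOVA against the completers interaction then has power of 98.8 against 94.1% (d = 0.50) and 92.0 against 80.4% (d = 0.40).

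**Type I error if either test could be claimed.** The null correlation of the two statistics is the square root of 1 over the variance ratio, which for completers is √((1 + ρ)/2). The probability that at least one exceeds 1.96 in absolute value, for ρ = 0.4 to 0.8, is 7.6, 7.3, 7.1, 6.8 and 6.5% for completers. For the mixed model it is 7.2, 7.0, 6.7, 6.5 and 6.2%. With the main test alone it is 5%.

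**The sentence on change.** Regressing change on arm and baseline gives the same treatment estimate and t statistic as regressing the Week 4 score on arm and baseline. If that sentence describes the main analysis run for one construct at a time, it adds no second test.

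**The case for a change.** The strongest case for a change is that the word *also* does not mean supportive, and that two analysts could both follow the plan and produce different tests of the per-construct change. The correlation is unknown and the plan covers many scales, so a high value cannot be presumed. With the completers' change score, ANCOVA and the interaction would fall on opposite sides of significance in 17.7% of trials at d = 0.40 and ρ = 0.4, and in 9.0% at d = 0.50. The remedy costs only a sentence or two.

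Part of this stands. The role and model of the interaction are unstated, and the sentence on change can be read two ways. But *main* set against *also* is an order, and it favours the more precise analysis. The sentence on change directly follows the main-analysis sentence and is most naturally read as that analysis repeated for each construct. The disagreement rates assume an interaction fitted to completers with free baseline means, which the plan does not specify. Where the two do disagree, the plan already says which is main.

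**Conclusion.** No change is needed. An analyst who follows the plan as written bases the conclusion on the baseline-adjusted Week 4 comparison, whose power and error rate are not affected by reporting an interaction beside it. Both analyses estimate the same effect under randomization, so bias is not in question.

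The interaction's loss of precision is real but modest: a variance ratio of 1.43 to 1.11 for completers, 1.28 to 1.07 in a mixed model using all baselines, and about 1 with constrained baseline means. At the stated d = 0.50 its lowest power in the range examined is 88.5%. The loss becomes material only at d = 0.40 with a correlation of 0.5 or less, and then only for the additional test. The 6.5 to 7.6% error rate needs a rule for claiming success that the plan does not contain. These figures rest on the assumed correlations, equal SDs and a two-sided 5% level; the mixed-model figures also assume follow-up missing completely at random.

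What remains is a gap in wording that analysts would fill sensibly, by treating change as the baseline-adjusted contrast and the interaction as supportive.
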